4.0 Resources and Personnel

The study will be conducted at two sites – Tampa VA and Bay Pines VA. Both sites will recruit from their primary hospitals, and also their respective CBOCs (outpatient clinics).

The key personnel's roles in the study are described in section 1.0. The only contractor is Vertical Product Development to create the explorer version of the App.

- Include where and by whom the research will be conducted.
- Provide a brief description of each individual's role in the study. Be sure to
 indicate who will have access to protected health information and who will be
 involved in recruiting subjects; obtaining informed consent; administering
 survey/interview procedures; and performing data analysis.
- If applicable provide information on any services that will be performed by contractors including what is being contracted out and with whom.
- If applicable provide information on any Memoranda of Understandings (MOUs) or Data Use Agreements (DUAs) that are being entered into including with whom and for what reason.

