5.0 Study Procedures

5.1 Study Design

- Describe experimental design of the study. Include sequential and/or parallel phases of the study, including durations, and explain which interventions are standard of care.
- Include a description of how anticipated risk will be minimized and include an analysis of risk vs. potential benefit.
- Provide description of the study population (delineate all categories of subjects – patients, providers, family members, employees, etc.). Include anticipated enrollment numbers
- As applicable, provide information on any added protections for vulnerable populations.
- If applicable include information on data.

Patients who meet eligibility criteria and consent to participate in the study are randomly assigned to one of two arms, either the Concussion Coach group, which will receive the Concussion Coach "Explorer" version either downloaded onto their own smart phone or via an iPod touch® given them for this purpose or the no mobile app control group. Study personnel will explain the purpose of the study, complete the informed consent process in person or over the telephone, obtain the random treatment assignment and introduce the participant to his/her baseline evaluator, if appropriate. The random assignment to intervention will be accomplished in blocks within each site. While small block sizes allow intervention group sizes to be very similar it may make the allocation process predictable. Therefore, to reduce selection bias and achieve balance across the intervention arms, a sequence list of individual assignments by random block sizes will be generated.

Both groups will be assessed in a pre/post intervention design and will be compensated for completing study questionnaires. During the time that they are involved in the study, the intervention group will be sent (via Concussion Coach) reminders to engage with the App. Their use (e.g., total time spent on each component of the App) will be collected electronically. Both

Version:13 05/31/2018

groups will receive care as usual (meaning their regularly scheduled VA appointments and medications). At the completion of the study, both groups will be encouraged to download the App for their own use, with assistance from the study team if needed (see Figure 2).

Description of Intervention & Training

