5.6 Data Analysis

[figure not shown]
Sample Size Justification: Below is a diagram of the expected subject recruitment and attrition (see Figure 2). Our recruitment estimates are based on our experience with prior trials (e.g., a recent pilot study of a web based intervention successfully recruited over 90% of potential participants) and our emphasis in the budget of recruitment personnel who will be embedded in our clinics. We conservatively estimate that 60% of potential participants will agree to participate and be successfully enrolled in the study. Our attrition estimate of 20% is based on our experience with an internet self-help intervention study, during which drop out was less than 20%. This was accomplished through continued outreach by the recruiter via letter and calls. Based on these conservative numbers and a recruiting period of 33 months we expect a minimum N=388 participants in the study [(20 newly identified participants per month over 33 months + 150 existing) *60% participation* (1-20% attrition)]. This is a conservative estimate

because we have excluded the existing 1,332 potential participants living in our area (national dataset) to whom we will mail letters.

For each regression model proposed for H1&2, results of sample size calculation using the application PASS v11 (Hintze, 2011) show that a much smaller N=148 (or N=194) achieves 80% (or 90%) power to detect an additional R-Squared of 0.05 (proportion of explained variation in the outcome) attributed to 2 independent variables (TBI Coach plus an interaction) using an F-Test with alpha of 0.05. This assumed the variables tested are adjusted for 10 independent variables with an R-Squared of 0.20.

We note that of all statistical models proposed in this study, the mediation model has the most stringent sample size requirement. With conservative total N=388, we expect to have greater than .80 power to detect a small to medium effect size of the mediated effect at alpha = 0.05. The two regression coefficients (beta1 & beta2) that jointly capture the mediated effects are critical in the power calculation for a mediation

Figure 2. Expected Total Recruitment

model. Using the parameter values of 0.14, 0.39, and 0.59, corresponding to Cohen's criteria68 for small (2% of the variance), medium (13% of the variance), and large (26% of the variance) effect sizes, respectively, Fritz and MacKinnon (2007) conducted empirical estimates of sample

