All data will be combined into a study database. The integrity of the database will be managed by our database manager. Analyses will be conducted by the statistician ([name]) and the PI ([name]).

Data Analysis Plan: An intention-to-treat (ITT) analysis will be performed, that is analysis will be based on the groups to which participants are randomized regardless of whether they receive or adhere to the assigned intervention. This will allow us to test the effects of assigning TBI Coach in practice, separate from assessing effects of adherence and/or loss to follow-up. Those who are lost to follow-up and therefore are missing outcome measures (T2 assessments) will be included in separate comparison analyses that utilize multiple imputations of the missing data.

For each primary outcome and other measures consisting of multiple items, a summation score will be produced for each subject. Summary of each variable by intervention group will be cross-tabulated. The time spent on TBI Coach and its specific components on the average will also be tabulated. All primary outcomes will be analyzed as continuous variables. Exploratory bivariate plots will be used to investigate possible nonlinear relationships between baseline/covariates and each follow up outcome variable. In separate statistical models proposed, we will control for demographics and other covariates including the baseline values of the outcome under investigation. Where appropriate, nonlinear regression model will be utilized (e.g., generalized additive model).

Hypothesis 1 (Primary Hypothesis): Patients randomized to receive TBI Coach for 3 months will have (a) lower post-concussive symptom severity and (b) lower psychological distress, compared to patients randomized to a no intervention control group, after adjusting for baseline severity and other potential confounders.

Analysis: The two intervention groups (TBI Coach = 1; Control = 0) will be compared on each outcome (a) and (b) in separate regression models that include the group variable and control for the outcome at baseline and other potential confounders. A significant positive estimated coefficient of the group variable will indicate positive TBI Coach's effects on the outcome, with the standardized value of the coefficient as the standardized effect size.

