Hypothesis 2: The effects of TBI Coach on PCS (and psychological distress) will be greater for Veterans who have (a) greater comfort with technology at baseline than for those who are less comfortable; (b) greater social support at baseline than for those with less social support.

Analysis: Two separate tests of moderated effects of TBI Coach will be performed with respect to each outcome. Each regression model in H1 (one per outcome) will be extended by adding a 2-way interaction term (between intervention and (a) eHealth Literacy Scale and (b) Social Support score; one at a time (i.e. two different moderation models per outcome). A significant coefficient of an interaction term will indicate presence of interactive effects. A co-plot using model fitted values will also be produced to further investigate the nature of any significant interaction.

Hypothesis 3: If TBI Coach improves Veterans' (a) knowledge about TBI and attribution of symptoms and/or (b) self-efficacy in coping with symptoms, Veterans will have less PCS and Psychological Distress.

Analysis: Single-mediator models⁷³ will test the indirect effects of the group variable (TBI Coach) on each outcome (separately) with respect to mediating variables: (a) knowledge and attribution, and (b) self-efficacy. Preliminary regression analyses will test whether (1) TBI Coach substantially changes the mediating variable, and (2) the mediating variable changes the outcome. Next, we will proceed to a full mediation model with simultaneous estimation of both direct and indirect effects of TBI Coach on the outcome. The mediated effect will be estimated as a product of the two path coefficients alpha and beta in the indirect pathway. The distribution of the product of coefficients is non-normal and this has implications for statistical inference as well as power calculation (see section on sample size justification). Therefore, the analysis will

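### Randomisation is blocked within two sites, but site is not named among the covariates of the H1 and H2 models (minor; free to fix)

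*Combined protocol and SAP*

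**What the plan says.** - **Design.** Section 4.0: "The study will be conducted at two sites", Tampa and Bay Pines. Section 5.1: participants are "randomly assigned to one of two arms", and "The random assignment to intervention will be accomplished in blocks within each site", with random block sizes. The allocation ratio is not stated.
- **Covariates in general.** Section 5.6, Data Analysis Plan: "we will control for demographics and other covariates including the baseline values of the outcome under investigation".
- **Hypothesis 1.** The arms are compared in "separate regression models that include the group variable and control for the outcome at baseline and other potential confounders".
- **Hypothesis 2.** "Each regression model in H1 (one per outcome) will be extended by adding a 2-way interaction term", so these models inherit whatever covariates H1 uses.
- **Power.** Section 5.6 allows for 10 adjustment variables with a joint R-squared of 0.20 and does not name them.

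Site is neither named nor ruled out in any of these places.

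**The concern.** Blocking within site balances the arms by site, so a difference in outcome level between Tampa and Bay Pines hardly enters the estimated group effect. A model without site still counts that difference as residual error. The reported standard error then exceeds the true sampling variability of the estimate, the confidence interval is wider than the design warrants, and the test rejects less often than its nominal level.

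The plan's wording does not bring site in by itself. Site is not a demographic characteristic, and because blocking balances it across arms it is not a confounder of the randomised comparison either. An analyst could follow the text faithfully and leave site out. Because the covariate list is open, the choice could also be made after the results are known.

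**Working it through.** **1. The plan's own figure.** Section 5.6 says its calculations "show that a much smaller N=148 (or N=194) achieves 80% (or 90%) power to detect an additional R-Squared of 0.05", for 2 tested variables adjusted for 10 others with R-squared 0.20, "using an F-Test with alpha of 0.05".

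- f² = 0.05 / (1 − 0.20 − 0.05) = 0.0667; degrees of freedom (2, N − 13); noncentrality N × f².
- N=148: noncentrality 9.87, power 0.8006. N=194: noncentrality 12.93, power 0.9016. Both stated figures reproduce.
- At the expected N=388: noncentrality 25.87, power 0.9971.

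**2. Cost of omitting site, main-effect test.** Assumptions: 1:1 allocation, N=388, and a true effect of d = 0.285 residual SD, chosen because it gives about 80% power. Let r be the share of residual variance (after baseline and other covariates) that site explains. No document gives r, so it is varied from 0 to 5%.

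- SE ratio = 1/√(1 − r)
- True type I error without site = 2[1 − Φ(1.96/√(1 − r))]
- L = d / √(4/388) = 2.807
- Power with site = Φ(L/√(1 − r) − 1.96)
- Power without site = Φ(L/√(1 − r) − 1.96/√(1 − r))

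| r | SE inflation | Type I error without site | Power without site | Power with site | Loss (points) |
|---|---|---|---|---|---|
| 0 | 0% | 0.050 | 80.1% | 80.1% | 0 |
| 1% | 0.5% | 0.049 | 80.3% | 80.5% | 0.3 |
| 2% | 1.0% | 0.048 | 80.4% | 80.9% | 0.5 |
| 5% | 2.6% | 0.044 | 80.8% | 82.1% | 1.4 |

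Losses are taken from unrounded values. With equal-sized sites, r = 0.25g²/(1 + 0.25g²) for a site gap of g within-site residual SD. So r = 1% means g of about 0.20, and r = 5% means g of about 0.46.

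**3. Simulation check.** Blocked randomisation within two sites, N=388, assumed 60/40 site split, baseline to follow-up correlation 0.6, 4,000 trials per setting.

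- Gap 0.5 residual SD, true effect 0.285: mean model SE 0.0838 without site and 0.0813 with it; the actual SD of the estimate was 0.0818 under both models. Power was 77.4% and 78.6%. With no true effect, rejection rates were 0.041 and 0.047.
- Gap 0.2 SD: SE 0.0816 and 0.0812; power 78.8% and 79.1%.
- No gap: the two models were practically identical.

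Monte Carlo error on each power figure is about √(0.8 × 0.2/4000) = 0.6 points. Both models were fitted to the same simulated trials, so the differences between them are more stable than the levels.

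**4. The same penalty on the plan's F test at N=388.** Dividing the critical value by (1 − r) changes power from 99.71% to 99.70% at r = 1% and 99.65% at r = 5%. If the group effect carried only half the stated increment (0.025 on 1 df, an assumption), power would change from 94.2% to 94.0% and 93.5%.

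**The case against.** **Site may already be intended.** The plan adjusts for other covariates, and its power calculation allows for ten unnamed variables; site could be one. This stands. A reader might infer that the plan leaves site out by decision, but the text supports only that site is unspecified.

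**The loss may be zero.** It arises only if site predicts the follow-up score beyond the baseline score and other covariates. Section 5.2 describes two Polytrauma Network Sites about 20 miles apart in the same VISN and allows telephone screening and consent, so for some participants site may reflect little more than which team enrolled them. This also stands. In the other direction, each site recruits from its own clinics, and Bay Pines has its own coordinator and email outreach, so a difference is possible. Neither consideration gives a size. A reader might infer that standard errors are certainly too large and power certainly lost; the documents do not support that.

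**The trial has power to spare.** For the stated R-squared increment, yes, as step 4 shows. The loss becomes visible only for smaller effects.

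**The argument does not cover every hypothesis.** A reader might extend it to H1 through H4. H4 is fitted in the app arm alone, so it has no randomised contrast. In H3 the path from mediator to outcome is not randomised; omitting site there raises possible confounding of unknown direction, not an inflated standard error. The figures above concern the main group effect only and show nothing for the H2 interaction, the mediated effect or the imputation.

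**Conclusion.** The gap is real but minor. Site stratifies the randomisation and is not named in the H1 or H2 models. If it is prognostic and left out, the error is on the conservative side: standard error up to 2.6% too large, type I error down to 0.044, and at most about 1.4 power points lost for an effect with about 80% power, for an assumed site share of up to 5%. With no site effect the loss is zero, and for the plan's stated target at N=388 it is negligible. A positive result would not be put in doubt.

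This rests on 1:1 allocation, the assumed range for the site share, and balance within site carrying through to the analysed sample. The case for acting is that the analysis should match the randomisation and that one open choice would be closed in advance. It does not rest on any demonstrated loss of power.

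**What to change.** In section 5.6, list site (Tampa or Bay Pines) as a prespecified fixed covariate in every H1 and H2 regression, and close the covariate list at the same time. For consistency, include site in the multiple-imputation model, so that it contains the analysis model's covariates, and in the H3 mediation equations. The standard-error argument gives no reason to change H4.

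The cost is one degree of freedom and one indicator the trial already holds. On the plan's own F test, a site term that explains nothing leaves power at 80.06% at N=148 to the precision shown, and one worth an R-squared of 0.01 raises it to 80.62%; at N=388 the latter moves power from 99.71% to 99.74%. Sample size and data collection do not change. The protocol's abstract reports recruitment as still under way, so the change could be made before the analysis.

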The Concussion Coach is designed to provide psychoeducation, self-assessment, and treatment of PCS following a mild TBI. The PI and three of the co-investigators were codevelopers of Concussion Coach. The public-facing Concussion Coach will be available for free download from a public marketplace and available for use with most mobile devices. The application has the advantage of privacy and anonymity, thus addressing the stigma often expressed as a barrier to seeking treatment. A mirror version of the public version, called Concussion Coach "Explorer Version", was developed and is being used for this study. Unlike the public version, it has the capacity to collect usage information, such as length of time spent on each part of the app, self-report ratings of symptoms and distress, and identification of "favorites" among the self-help tools. This data can be uploaded in a de-identified form to a HIPAA compliant server. Other than the ability to collect data, it will be exactly like the "real" Concussion Coach. The Explorer version will be developed by our collaborators, Vertical Product Development, which developed Concussion Coach, PTSD Coach, and PTSD Explorer version. Explorer versions are especially useful as they allow for unobtrusive, highly detailed, real-time data collection without relying on patient self-report. In addition, the Concussion Coach will be an 'opportunistic' exporter of data. It will upload data to the server whenever it has new data and is in a Wi-Fi zone; participants do not have to have a home wireless network. If they never enter a Wi-Fi area, we will collect the data from their smart phone or iPod device at the second and final study visit. We will utilize ohmage, an existing open source technology stack. to port the app to the server.

Concussion Coach has the following components in addition to a 'Resources' section:

- Psychoeducational content covering basic information about mild TBI, associated symptoms, and resources for additional help. The information is derived from various VA and DoD informational websites and is based on the scientific literature on TBI. There are approximately 10 headings (e.g., "What is TBI?") that can be clicked to receive educational information. Additionally, each answer includes an icon, visually represented by an ear that the user may tap in order to hear the information spoken aloud.
- Self-assessment using the Neurobehavioral Symptom Inventory (NSI), a validated measure

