Data Collection Methods: After informed consent and randomization, participants will complete baseline study measures. At follow-up, participants will be re-assessed using the same measures via mail, telephone or in person with telephone reminders, if needed. In addition, Concussion Coach will also collect the extent of their interaction with the application during their participation.

Individual interviews will be conducted with at least 10% of the Concussion Coach users to evaluate their perception and satisfaction with other TBI-related education received within the VA to date, their overall satisfaction with Concussion Coach e.g. its ease of use, perceived barriers and facilitators to the use of the App, behavioral intention to use Concussion Coach in the future and recommendations for improving it. This 10% sample will not be random – rather we will solicit interviews from those who improved using PCS Concussion Coach, those who did not get better or became worse, and those who did not use the App during the study period or used it infrequently. In addition to qualitative questions about barriers and facilitators, interview questions will include quantitative assessment of satisfaction (e.g., rating scales of satisfaction). Interviews will be conducted by experienced trained interviewers (e.g., [name]) and will be audio recorded. Participants will already be consented in person or over the telephone, so the interviewer will identify and briefly recap the consenting process, the project, and then ask permission for audio tape recording the interview. Interviews will be conducted by phone or in person based on participant convenience. The interviewer will use standard communication techniques to stimulate discussion such as generic prompts (tell me more), summarizing statements, silence, and eye contact. If the respondent exhibits adverse reactions, such as shame, during the interview, every effort will be made to encourage him or her and they will be reminded of their rights as participants.

Risk Minimization Plan:

The educational program is self-administered and participation is strictly voluntary. There are no known risks involved. The PI will inform participants of all methods used to maintain confidentiality of information. Participants will be assured of the confidentiality of the data and that no one outside of the research team will have access to the raw data.

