It is possible that potential participants will not be able to meet in person and will need to talk to a study investigator via telephone. In this instance, a study investigator will explain the study determine that the participant is interested in participating, and screen for eligibility. If eligible, an appointment will be scheduled for the participant to meet in-person with the study team members to complete the consenting process. Or, for interested participants who reside a distance away from the VA and would like to participate in the study the ICF will be done over the telephone. After the Telephone Consent process is complete, a copy of the study ICF/Information Sheet will be mailed to the participant for his/her file. Once the consent process is completed via telephone with those participants who are not able to physically be at either the Tampa or Bay Pines VA site location, they will be asked to complete the study Baseline questionnaires. When speaking to potential participants via telephone, the study team member will be physically located at the Tampa or Bay Pines VA.

To facilitate the recruitment process, we will hang flyers throughout the hospitals and catchment area (e.g., outpatient clinics) of each hospital, and provide the clinical team with hospital-based flyers and business cards to give to interested patients. (See the Appendix for the hospital-based flyer and business card.)

Relevant Veteran Events: With permission from event organizer(s) and/or department manager(s), we will attend and/or contribute to relevant events around the Tampa/St. Petersburg area. Methods of recruitment during events may include but are not limited to, providing flyers, cards, and/or give-away recruitment materials. It may also involve giving a short presentation on the participation opportunities, collecting contact information from interested participants, or leaving a basket of give-away recruitment materials at a desk for interested participants to pick up at their leisure (the flyers, business cards, and give-away recruitment

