be performed using the Mplus statistical application which offers alternatives that do not require the regular assumption of symmetric, normal distributions for parameter estimates. Bayesian estimation method with diffuse priors will be used with appropriate posterior simulation schemes based in Markov Chain Monte Carlo (MCMC) methods. One advantage of the MCMC estimation process is that it provides accurate tests of mediated effects for small samples; e.g. by simply taking the product of the two coefficients alpha and beta for every draw and compute its standard deviation across all draws to obtain standard errors of mediated effect. Also, unlike the normal-based ML confidence interval, inference will rely on Bayesian credibility interval based on the percentiles of the posterior, which easily allows for a strongly skewed distribution alphabeta product⁷⁴

Hypothesis 4: More time spent on (a) TBI Coach use, and (b) specific interactive components of TBI Coach (i.e., the "tools" section) will be associated with lower PCS symptom severity after adjusting for baseline PCS values and potential confounders.

Analysis: A regression model of PCS will be performed on the TBI Coach sample only, separately for (a) TBI coach use, and (b) each interactive component as the main predictor. First the PCS baseline score, demographics and other potential confounders will be included in the base model. Then a full model with addition of the time score for one TBI Coach aspect at a time will be fitted. Appropriate transformation (e.g. log) of all time variables will be done as suggested by their general distribution; a significant negative coefficient of the time variable will confirm a negative association between time spent on that component and symptom severity. Standardized coefficient estimates as well as R-sq estimates will be obtained so that all TBI Coach aspect-specific models can be compared on the relative strengths of the aspect-outcome relationships.

As an extension, secondary analysis will be performed on the TBI Coach components that show strong relationship in the expected direction. Each time spent (as a dependent variable) will be regressed on the predictors in the base model to identify both positive and negative contributory factors to the specific component usage.

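### The fallback for app-use data that never upload needs an in-person final visit, so it cannot work when follow-up is by mail or telephone, and Hypothesis 4 loses those participants' use data

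*Combined protocol and SAP*

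**What the plan says.** **Upload.** Section 5.1, Description of Intervention & Training, describes the Explorer version of the app: "It will upload data to the server whenever it has new data and is in a Wi-Fi zone". A home network is not required. The fallback has a condition, "If they never enter a Wi-Fi area", and then an action: "we will collect the data from their smart phone or iPod device at the second and final study visit".

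**Follow-up mode.** Section 5.1, Data Collection Methods, says that at follow-up "participants will be re-assessed using the same measures via mail, telephone or in person with telephone reminders, if needed".

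**Remote enrolment.** Section 5.2 provides that for interested people living at a distance "the ICF will be done over the telephone". It goes on to describe baseline questionnaires for "those participants who are not able to physically be at either the Tampa or Bay Pines VA site location".

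**Use of the data.** Table 1 (Section 5.5) gives the app download as the source for time on the app and on its components. Section 5.6 says of Hypothesis 4: "A regression model of PCS will be performed on the TBI Coach sample only". Time scores are entered one app aspect at a time. Sections 5.1 and 5.5 also plan interviews with "those who did not use the App during the study period or used it infrequently".

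**Missing data.** Section 5.6 provides multiple imputation for missing follow-up outcomes. It has no rule for missing use time.

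**The concern.** The fallback assumes that everyone attends a final visit, whereas the rest of the protocol allows a participant to be consented, assessed at baseline and followed up without ever attending. For such a person, data still on the device at the end of the study have no stated way of reaching the trial.

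Two things are at stake, both outside the primary analysis. Hypothesis 4, and the research question on which app components help, lose exposure data. And because nothing states how an absent record is to be read, whoever builds the dataset must choose between missing and zero, two choices with very different consequences. The same ambiguity reaches the interview sample: someone whose log never arrived could be approached as a non-user and asked about barriers to use.

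**Working it through.** **1. Can the fallback operate in each follow-up mode?**

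| Follow-up | Data uploaded by Wi-Fi | Data still on device |
|---|---|---|
| In person | on the server | read from the device (Section 5.1 fallback) |
| Telephone | on the server | no stated route |
| Mail | on the server | no stated route |

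No section mentions device return, a prompted upload or a server check. The fallback's condition also covers only people who never reach Wi-Fi. Sessions logged after a last successful upload have no stated route either.

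**2. The sample available to Hypothesis 4.** Section 5.6 expects (20 × 33 + 150) × 0.60 × 0.80 = 388.8, which reproduces its 388. Its regression sample sizes also reproduce. With f² = 0.05/(1 − 0.05 − 0.20) = 0.0667, two tested variables, 10 covariates and noncentrality N·f², the F-test needs N = 148 for 80% power and N = 194 for 90%. Neither figure is in dispute. Assuming 1:1 allocation (the ratio is not stated), the app arm has 388/2 = 194.

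**3. Illustration: affected records treated as missing.** Assumptions: one time variable with R² 0.05, 10 covariates with R² 0.20, loss at random, affected share 5% to 30%. The share is not in the documents. Noncentrality at n = 194 is 194 × 0.0667 = 12.9 on 1 and 182 degrees of freedom.

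| Affected share | n | Power |
|---|---|---|
| 0% | 194 | 94.7% |
| 5% | 184 | 93.6% |
| 10% | 175 | 92.4% |
| 20% | 155 | 89.1% |
| 30% | 136 | 84.8% |

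Under these assumptions the slope is unbiased.

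**4. Illustration: affected records coded as zero.** The plan does not say this; it is the other choice left open. Let x = log(1 + minutes), with mean μ and variance σ² in the app arm, and let a share q be set to zero at random. Then Cov(x_obs, x) = (1 − q)σ² and Var(x_obs) = (1 − q)(σ² + qμ²), so the fraction of the slope kept is 1/(1 + q·μ²/σ²).

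Assume log-normal minutes among users (median 30, log SD 1) and 15% true non-users. Among users, x has mean 3.453 and mean square 12.828 by numerical integration. So μ = 0.85 × 3.453 = 2.935, σ² = 0.85 × 12.828 − 2.935² = 2.29, and μ²/σ² = 3.76. Power comes from 4,000 simulated trials per setting, with one baseline covariate (R² 0.20).

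| q | Slope kept, formula | Slope kept, simulated | Power, simulated |
|---|---|---|---|
| 0% | 1.00 | 1.00 | 94% |
| 5% | 0.84 | 0.84 | 88% |
| 10% | 0.73 | 0.73 | 82% |
| 20% | 0.57 | 0.58 | 66% |
| 30% | 0.47 | 0.47 | 52% |

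**5. Sensitivity to the share of true non-users.** At q = 10%, the formula keeps 1/(1 + 0.10 × 13.16) = 0.43 of the slope with no true non-users, 0.73 with 15%, and 1/(1 + 0.10 × 1.86) = 0.84 with 30%. At q = 1% with 15% true non-users, it keeps 1/(1 + 0.01 × 3.76) = 0.96.

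**The case against.** The strongest reply is about reach. The gap needs three things together: assignment to the app, data that never reached a Wi-Fi zone, and no in-person follow-up. Any Wi-Fi zone suffices, so most mail and telephone participants may upload without help. A reader might infer that all remotely followed participants lose their use data; the documents do not support that, and they give no share from which to size the loss. This part of the objection stands.

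Second, nothing says that a participant without an upload is scored as zero use. On the natural reading the predictor is absent, and step 3 shows a modest cost. The attenuation in step 4 follows only if the dataset makes a choice that the plan neither prescribes nor rules out. This stands too.

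Third, partial safeguards exist. The Follow-Up Data Form in Table 1 has an item on app use that does not depend on upload. App data go periodically to study staff under a study number, so absent uploads could be noticed. The interview itself would probably reveal a misclassified user. But the form's content is not described, it is listed as a potential moderator and not as a source for Hypothesis 4, and no section tells staff to act on an absent upload. These safeguards soften the gap without closing it.

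Fourth, it is tempting to say that the loss falls on the very group whose access the trial aims to improve. Sections 2.0 and 5.2 show that distance and access are real issues, but the stated goal in Section 3.0 concerns Veterans with persisting symptoms, not people without Wi-Fi. Non-random loss is plausible, not shown.

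**Conclusion.** The concern holds in a limited form. A stated retrieval rule cannot operate for two of the three permitted follow-up modes, and no other route is given. App-arm participants with un-uploaded data and no in-person follow-up are lost to Hypothesis 4 as an exposure record, and the plan does not say how their use time is to be handled.

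The size is unknown. If few are affected, the effect is negligible. Over an assumed 5% to 30%, with 194 in the app arm, true R² 0.05 and loss at random, treating use as missing costs about 1 to 10 points of power and no bias. Zero-coding would keep about 84% to 47% of the slope if 15% are true non-users, and the result depends heavily on that share. These ranges show why the rule matters; they do not forecast this trial.

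The primary intention-to-treat comparison (Hypothesis 1) uses no app data and is unaffected. The point merits correction because the remedy is cheap, and the rule on missing versus zero can still be applied to everyone in the app arm at analysis.

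**What to change.** **Section 5.1, Description of Intervention & Training.** Make the fallback work in every follow-up mode. At the follow-up contact, by mail, telephone or in person, ask the participant to connect the device to any Wi-Fi network so that stored data upload, and check the server for the upload. Apply this to anyone with data left on the device, not only those who never reached Wi-Fi. Exclude sessions logged on or after that contact from use time, so that the prompt itself does not count as use.

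**Section 5.6, Hypothesis 4.** Record upload status for each app-arm participant.
- Code use time as zero when an upload shows no sessions before the follow-up contact, or when the participant confirms at follow-up, for example on the Follow-Up Data Form, that the app was never used.
- Treat it as missing when there is no upload and non-use is not confirmed.

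The self-report route to zero is needed because the app uploads only when it has new data, so a true non-user may never produce an upload. Accepting zero only from an upload would turn true non-users into missing and remove the low end of the exposure range.

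**Interviews (Sections 5.1 and 5.5).** Select non-users and infrequent users from those with confirmed non-use or low use.

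**Cost.** An added line in the follow-up call or letter, a server check and a data rule. A few app-arm participants will be missing from Hypothesis 4, and some zeros will rest on self-report.
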